### **5.3.1.2 General Exclusion Criteria**

1. Subject with an indication for the index procedure of acute ST-segment elevation MI (STEMI).
2. Subject has a known hypersensitivity or contraindication to aspirin, heparin/bivalirudin, P2Y12 inhibitors (clopidogrel/prasugrel/ticagrelor), everolimus, cobalt, chromium, nickel, tungsten, acrylic and fluoro polymers or contrast sensitivity that cannot be adequately pre-medicated.
3. Subject with implantation of another drug-eluting stent (other than XIENCE) within 9 months prior to index procedure.
4. Subject has a known left ventricular ejection fraction (LVEF)  $<30\%$ .
5. Subject judged by physician as inappropriate for discontinuation from P2Y12 inhibitor use at 3 months, due to another condition requiring chronic P2Y12 inhibitor use.

6. Subject with planned surgery or procedure necessitating discontinuation of P2Y12 inhibitor within 3 months following index procedure.
7. Subject with a current medical condition with a life expectancy of less than 12 months
8. Subject intends to participate in an investigational drug or device trial within 12 months following the index procedure.
9. Pregnant or nursing subjects and those who plan pregnancy in the period up to 1 year following index procedure. Female subjects of child-bearing potential must have a negative pregnancy test done within 7 days prior to the index procedure per site standard test.

**Note:** Female patients of childbearing potential should be instructed to use safe contraception (e.g., intrauterine devices, hormonal contraceptives: contraceptive pills, implants, transdermal patches, hormonal vaginal devices, injections with prolonged release.) It is accepted, in certain cases, to include subjects having a sterilised regular partner or subjects using a double barrier contraceptive method. However, this should be explicitly justified in special circumstances arising from the study design, product characteristics and/or study population.

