## 9.2 Analysis Populations

The primary analysis population is “3-month clear” population, defined as subjects who are free from myocardial infarction (modified ARC), repeat coronary revascularization, stroke, or stent thrombosis (ARC definite/probable) within 3 months (prior to 3-month visit but at least 90 days) after stenting AND have been compliant with 3-month dual antiplatelet therapy (DAPT) without interruption of either aspirin and/or P2Y12 receptor inhibitor for > 7 consecutive days.

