## APPENDIX IV: SCHEDULE OF EVENTS

[figure not shown]
PROCEDURE/TEST	Baseline	Pre-Procedure (within 24 hours)	Procedure	Post-Procedure	3-month ( $\pm$ 7d) Office visit 	6-month ( $\pm$ 14d) Office visit or phone contact 	12-month ( $\pm$ 28d) Office visit or phone contact 	Unscheduled visits
Subject Medical/Clinical History (Age, Sex, Risk Factors, Cardiac Status, Cardiac History)	✓							
Subject Informed Consent (Must be obtained prior to any study related testing or procedures)	✓							
General Inclusion/Exclusion Criteria	✓							
Angiographic Inclusion/Exclusion Criteria			✓					
Coronary Angiogram			✓					
Study Stent and Procedure Information			✓					
Antiplatelet Medications Loading Dose		✓	✓					
P2Y12 Inhibitor Discontinuation Eligibility Assessment					✓			
Post-procedure Antiplatelet Medications 				✓	✓	✓	✓	✓
Adverse Events			✓	✓	✓	✓	✓	✓

Subject who are “3-month clear” will discontinue P2Y12 inhibitor after 3-month visit, but continue taking aspirin through 12-month follow-up. Subjects who are not eligible for early P2Y12 inhibitor discontinuation will be treated per site standard of care.

Office visit is required for 3-month follow-up. A formal office visit is required at 3-month follow-up to ensure a thorough clinical evaluation. A telephone contact is an option only for subjects who would otherwise be lost to follow-up due to being unable to complete an office visit, but a formal follow-up visit is still preferred at 3 months.

Office visit is strongly recommended whenever possible.

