1.3 Study Design

XIENCE 90 study is a prospective, single arm, multi-center, open label trial to evaluate the safety of 3-month dual antiplatelet therapy (DAPT) in subjects at high risk of bleeding (HBR) undergoing percutaneous coronary intervention (PCI) with the approved XIENCE family of coronary drug-eluting stents.

The XIENCE family stent systems include commercially approved^a XIENCE Xpedition Everolimus Eluting Coronary Stent System (EECSS), XIENCE Alpine EECSS or XIENCE PRO^X EECSS (OUS only)^b, XIENCE PRO^A EECSS (OUS only)^c, and XIENCE Sierra EECSS,

^a The commercially approved XIENCE stent will be used in geographies where it is commercially available

^b XIENCE PRO^X is a rebrand of the XIENCE Xpedition Stent System and is only available outside of the United States.

^c XIENCE PRO^A is a rebrand of the XIENCE Alpine Stent System and is only available outside of the United States.

which are all manufactured by Abbott Vascular, Inc, Santa Clara, USA. The above XIENCE family stent systems will hereinafter be called “XIENCE” in this study.

Approximately 2,000 subjects from approximately 100 sites globally will be registered in this study, with at least 50% of subjects in the United States (US). Study population consists of non-complex HBR subjects with up to three native coronary artery lesions (a maximum of two lesions per epicardial vessel) with reference vessel diameter between 2.25 mm and 4.25 mm. Eligibility of P2Y12 receptor inhibitor discontinuation will be assessed at 3-month follow-up. Subjects who are free from myocardial infarction (modified ARC), repeat coronary revascularization, stroke, or stent thrombosis (ARC definite/probable) within 3 months (prior to 3-month visit but at least 90 days) after stenting AND have been compliant with 3-month DAPT without interruption of either aspirin and/or P2Y12 receptor inhibitor for > 7 consecutive days are considered as “3-month clear”, and will discontinue P2Y12 receptor inhibitor and continued with aspirin monotherapy after 3-month follow-up.

All registered subjects will be followed at 3, 6 and 12 months post index procedure.

The data collected from the XIENCE 90 study will be compared with the historical control of non-complex HBR subjects treated with standard DAPT duration of up to 12 months from the XIENCE V USA study, which is a US post-approval study to evaluate the safety of XIENCE V EECSS in “all-comer” population under real-world setting.

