1.4 Analysis Populations

Primary Analysis Population

The primary analysis population includes “3-month clear” population, defined as subjects who are free from myocardial infarction (modified ARC), repeat coronary revascularization, stroke, or stent thrombosis (ARC definite/probable) within 3 months [REDACTED]

[REDACTED] after stenting AND have been compliant with 3-month dual antiplatelet therapy

(DAPT) [REDACTED]

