2.9 Sensitivity Analysis

The primary and major secondary endpoints between 3-month and 12-month follow-up will be analyzed descriptively for the 3-month clear population removing the patients who do not have antiplatelet medication compliance after 3 months.

For the 3-month DAPT arm, antiplatelet medication non-compliance beyond 3-month follow-up for 3-month clear population is defined as patients who resume P2Y12 inhibitor for more than 7 consecutive days, and/or interrupt aspirin for more than 7 consecutive days between 3-month and 12-month follow up.

[REDACTED]

[REDACTED]

[REDACTED]

[REDACTED]

[REDACTED]

[REDACTED]

[REDACTED]

In addition, a sensitivity analysis will be performed for the primary endpoint analysis to evaluate the impact of the missing outcome. The analysis will be carried out based on the primary analysis population, and by imputing the missing outcomes for each imputed baseline PS dataset, and Rubin's combination rule [29] will be used to consolidate the final analysis for the 10 duplicates of the imputed dataset. Refer to Appendix A for more details.

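### As visible, SAP 2.9 counts only resumed P2Y12 inhibitor use as non-compliance in XIENCE 90, so 3-month-clear subjects who never stop the drug stay in the descriptive adherence set

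*SAP*

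**What the plan says.** SAP 2.9 states that the primary and major secondary endpoints between 3 and 12 months "will be analyzed descriptively for the 3-month clear population removing the patients who do not have antiplatelet medication compliance after 3 months". It then defines non-compliance for the 3-month DAPT arm as "patients who resume P2Y12 inhibitor for more than 7 consecutive days, and/or interrupt aspirin for more than 7 consecutive days", within the 3- to 12-month interval. Redacted text follows that definition.

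The strategy under test is discontinuation. SAP 1.3 says that 3-month-clear subjects "will discontinue P2Y12 receptor inhibitor and continued with aspirin monotherapy after 3-month follow-up". Footnote 1 to Protocol Appendix IV says that they "will discontinue P2Y12 inhibitor after 3-month visit, but continue taking aspirin through 12-month follow-up", and Protocol 6.3.2 gives the same instruction. None of these places states how soon after the visit the stop must occur.

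Entry to the population looks backwards from 3 months. Besides freedom from the listed events, Protocol 9.2 requires that subjects "have been compliant with 3-month dual antiplatelet therapy (DAPT) without interruption of either aspirin and/or P2Y12 receptor inhibitor for > 7 consecutive days". An actual stop at 3 months is not a condition. The matching text in SAP 1.4 can be read as far as "after stenting AND have been compliant with 3-month dual antiplatelet therapy" and is redacted soon after.

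**The concern.** An adherence analysis should show outcomes in those who followed the assigned regimen. For the XIENCE 90 arm that means aspirin alone after the 3-month assessment. A definition built on resuming catches those who stopped and went back, but not those who never stopped. The longest departure from the regimen is then classed as compliant, and a much shorter one is not.

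This is the only analysis of adherence after 3 months that can be seen in the SAP. The primary objective is non-inferiority, and departures that make the two groups more alike can favour that conclusion. A set that separates out true discontinuers would be a useful check. As worded, this set may not do so.

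**Working it through.** The plan gives no figure to reproduce here. The check is of logic, with some day arithmetic.

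**Four 3-month-clear profiles, all with uninterrupted aspirin, against the visible SAP 2.9 definition**

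- Stops at the 3-month assessment and stays off: not resumed, so kept. This matches the strategy.
- Stops, then takes the drug again for more than 7 consecutive days: resumed, so removed. This matches the purpose of the analysis.
- Never stops through 12 months: no stop, hence no resumption, so kept. This is contrary to the strategy.
- First stops some time after the 3-month assessment and stays off: no resumption, so kept. Whether this departs from the strategy depends on a cut-off that the documents do not give.

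Protocol 9.2 does not screen out the third and fourth profiles, because it looks only at the first 3 months.

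**Exposure that the rule tolerates.** Inputs are the visit days 90, 180 and 365 in Protocol 6.4. The interval is 365 − 90 = 275 days.

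- Shortest resumption in whole days that removes a subject: 8/275 = 2.9% of the interval.
- First stop at day 180, chosen only as an example: (180 − 90)/275 = 90/275 = 32.7%, kept.
- Never stops: 275/275 = 100%, kept.

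These are shares of exposure time, not effects on any result.

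**Why an anchor day is needed.** The 3-month visit window is 90 ± 7 days. An allowance of 7 days counted from day 90 ends on day 97, which is already the last day of the window. Counted from a visit on day 97, it ends on day 97 + 7 = 104. The two anchors can differ by 7 days.

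**Possible effect, by assumption only.** Suppose a share q of the retained XIENCE 90 set never stops, stoppers differ from control by D, continuers differ by kD, and the control rate is fixed. The set then shows (1 − q)D + qkD = D[1 − q(1 − k)]. For q = 5%, 10% and 20%:

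- k = 0 (continuers like control): 0.95, 0.90 and 0.80 of D.
- k = 0.5: 0.975, 0.95 and 0.90 of D.
- k = 1.5 (continuers differ more than stoppers): 1.025, 1.05 and 1.10 of D.

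Neither q nor k has a source in the documents. D is the difference among stoppers in an already selected set. The expression concerns death/MI and bleeding, for which the plan has a control comparison. Stent thrombosis is judged against a performance goal (SAP 2.1.4 and 2.2.2), so there the retained set's rate is simply a mixture of stoppers' and continuers' rates.

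**The case against.** **Redaction.** The claim that no rule removes continuers rests on text next to blacked-out blocks in SAP 1.4 and 2.9, and a further rule could sit there. This stands as a limit on confidence. However, the visible XIENCE 90 sentence reads as a complete definition, and the hidden text may only deal with the control arm.

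**Wording.** The opening sentence of SAP 2.9 removes subjects who lack compliance after 3 months, and someone told to stop who does not is non-compliant in the ordinary sense. The drafter may have assumed that every eligible subject had stopped. That is a plausible intention, but an explicit definition normally governs the general phrase before it. If this is what was meant, the remedy is to write it.

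**Rarity.** Protocol 5.3.1.1 item 4 requires agreement to stop, and item 5 of Protocol 5.3.1.2 excludes a "Subject judged by physician as inappropriate for discontinuation from P2Y12 inhibitor use at 3 months, due to another condition requiring chronic P2Y12 inhibitor use". Protocol 11.5 lists treatment compliance among major deviations. These provisions should make continuation less common, but none takes a continuer out of the set. The trial is open label, and the Protocol 6.3.2 note on 12 months of prasugrel for some subjects does not say whether it is limited to those who are not 3-month clear. I take no position on that clinical rule.

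**Stronger readings that the documents do not support.**

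- A reader might infer that the non-inferiority test is biased by this definition. It is not, because the tests in SAP 2.1.4, 2.2.1 and 2.2.2 use the full primary analysis population.
- A reader might infer that an arm difference in stent thrombosis is diluted. The planned stent thrombosis test has no control arm.
- A reader might infer that every late stopper breaks the plan. No maximum delay is stated.
- A reader might infer that continuers are on the control regimen. SAP 1.3 describes a "historical control of non-complex HBR subjects treated with standard DAPT duration of up to 12 months", so control exposure itself varied.

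**Conclusion.** On the visible text the point holds. SAP 2.9 keeps as compliant a 3-month-clear subject who takes aspirin without a gap and never stops the P2Y12 inhibitor. It also keeps late stoppers, for whom the sponsor must set the cut-off because the documents have none.

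The consequence is confined to a descriptive analysis. No test, significance level or sample size changes. Keeping continuers could blur the death/MI and bleeding comparison with control, and the XIENCE 90 stent thrombosis rate in the adherence set. If continuers have control-like risk, the comparison shrinks. If they continue because of higher ischaemic risk, it could move the other way. Neither size nor direction can be given, since the documents report no non-stopping rate. The ratios of 0.80 to 1.10 above rest wholly on assumed values and a fixed control rate, although SAP 2.9 may also remove controls under a rule that cannot be seen.

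Severity is minor. Confidence is low to medium because of the redactions and the looser reading of the word resume.

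**What to change.** In SAP 2.9, define non-compliance in the XIENCE 90 arm as either of the following:

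- any P2Y12 inhibitor use after the 3-month assessment, whether continued or resumed, that exceeds an analysis allowance set by the sponsor. The SAP's own 7 consecutive days is one option;
- interruption of aspirin for more than 7 consecutive days, as now.

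State the day from which the allowance is counted, taking account of the ± 7 day visit window and of missed visits (Protocol 5.5). Report how many 3-month-clear subjects never stopped, stopped late or resumed. Add that the set is selected on behaviour after 3 months, so it is supportive only.

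This changes how subjects are classified for one analysis and alters no treatment rule. The cost is one sentence and one row of counts. Protocol 6.3.2 already has P2Y12 start and stop dates on the eCRF, so no new data are needed. If redacted text already covers continued use, the sponsor need only confirm it.

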2.10 Documentation and Other Considerations

All analyses will be performed using SAS® for Windows, version 9.1 or higher.

3. ACRONYMS AND ABBREVIATIONS

Acronym or Abbreviation	Complete Phrase or Definition
ACS	Acute Coronary Syndrome
AMI	Acute Myocardial Infarction
ARC	Academic Research Consortium
BARC	Bleeding Academic Research Consortium
BMI	Body Mass Index
CABG	Coronary artery bypass grafting
CTO	Chronic Total Occlusion
DAPT	Dual Antiplatelet Therapy
DMR	Death/MI/Revascularization
EECSS	Everolimus Eluting Coronary Stent System
Hb	Hemoglobin
HBR	High Bleeding Risk
LVEF	Left Ventricular Ejection Fraction
MI	Myocardial Infarction
NSTEMI	non ST-segment elevation MI
PCI	Percutaneous Coronary Syndrome
PS	Propensity Score
RVD	Reference Vessel Diameter
SAP	Statistical Analysis Plan
ST	Stent Thrombosis
STEMI	ST-segment elevation myocardial infarction
TLF	Target Lesion Failure
TLR	Target Lesion Revascularization
TVR	Target Vessel Revascularization
US	United State

